3.2 END OF STUDY DEFINITION

While Primary Completion will be defined as the date of the last 12-month assessment data collection of the last participant, the End of Study will be the date that caregiver-child benchmark data and home visit completion data have been received from our home visiting program partner, as these data will provide necessary covariates for the conduct of our statistical analyses and are needed to ensure the study does not affect family services

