2.3 RISK/BENEFIT ASSESSMENT

2.3.1 KNOWN POTENTIAL RISKS

This study involves providing a health behavior intervention to low-income mothers or primary caregivers and children; therefore, the use of children as participants is inherent to the nature of this protocol. If a mother becomes pregnant during the course of the study, we decided not to exclude or discontinue her from the study, as the habit behaviors pose no risk and are likely beneficial to her as well as her unborn child but are also primarily aimed at providing healthy options for the child in the study. The study intervention, which is aimed to improve health behaviors of mothers or primary caregivers and children, is considered low-risk. Additionally, because the study assessments only involve completion of interviews, surveys, vitals, and home food assessments, there is still less than minimal risk to participants. There is a low risk of emotional or psychological discomfort from participants answering personal questions about their eating and activity behaviors. There is also a possible minimal, mild, and temporary risk for physical overexertion due to exercise from increased walking and physical activity. To protect the rights and welfare of these participants, they will be assured that their regular home *visiting* services will in no way be affected by their decision to participate, or not participate, in the study. While we are offering financial incentives to mothers or primary caregivers, these incentives are modest and are only intended to compensate for time completing assessments.

In our preliminary work providing these services, mothers or primary caregivers did not report increased burden from participating in this program. Participants receiving the obesity prevention curriculum were just as likely to meet the benchmark areas defined by Health Resources and Services Administration for evaluating the conventional home visiting program, which suggests that the additional obesity prevention content did not detract from the existing services or over-burden participants receiving the combined program. Also, participants were 27% less likely to discontinue home visiting services when they received the combined home visiting + obesity prevention curriculum as compared to those receiving the conventional program alone in our prior preliminary work.

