3 STUDY DESIGN

3.1 OVERALL DESIGN

This is a cluster randomized trial in which home visitors (n=18 anticipated) employed by our partner (First Teach Home Visiting Program) will be randomly assigned to deliver the home visiting standard curriculum with or without HABITS (n=9 home visitors in each arm).

Caregivers with a child 0-5 years of age who are enrolled in the First Teacher Home Visiting program and who have completed their initial 90-day home visiting program benchmark testing will constitute our initial recruitment pool (>50% African American, 40% White, <10% other/multiple race). First Teacher Home Visiting Program enrolls caregivers with young children in their free and voluntary services through community outreach. In order to be eligible for home visiting services, families must have a social risk factor such as poverty, social isolation, lack of material and social support, lack of transportation and limited education and literacy.

Home visitors will approach their families who are potentially eligible to introduce the study, gauge interest, and screen interested families for eligibility. Designated study staff determine of families are eligible based on the completed screening form and inclusion/exclusion criteria. Home visitors are informed of family's eligibility and notify the family. Eligible families are then introduced to a blinded study assessment worker who schedules the enrollment and baseline visit.

Assessment workers (who are distinct from home visitors and masked to group assignment) will be responsible for completing informed consent, enrolling caregiver-child dyads into the study, and completing Visit 1 (baseline), Visit 2 (6-month), and Visit 3 (12-month) assessments.

After completing Visit 1 (baseline) assessment procedures, families will be told by their home visitor which study arm they have been allocated to, for those in the HABITS intervention arm (i.e., home visiting standard curriculum with HABITS) will begin receiving the HABITS intervention at their home visits for 12-months.

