6 STUDY INTERVENTION DISCONTINUATION AND SUBJECT DISCONTINUATION/WITHDRAWAL

6.1 DISCONTINUATION OF STUDY INTERVENTION

Participants will continue to receive the study intervention for the 12-month trial, as long as they remain in the home visiting program. The study intervention may be discontinued for a participant if a clinical adverse event (AE) or other medical condition or situation occurs such that continued participation in the study intervention would not be in the best interest of the subject.

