- Food and Activity Frequency Survey (All 3 visits): To best capture maternal feeding practices related to behaviors targeted by HABITS, mothers will complete modified versions of the Children's Dietary Questionnaire⁸⁰ and Diet and Behavior Questionnaire (DBQ)⁸¹ of the National Health and Nutrition Examination Survey. These instruments will be modified to focus on the eating behaviors targeted by HABITS: SSB, fried foods, and fruits and vegetables.
- Home Food and Activity Environment Assessment (All 3 visits): A modified version of the Home Food Assessment (HFA) and Home-Inventory Describing Eating and Activity Development (Home-IDEA) adapted to HABITS target behaviors will be used by assessment workers to assess accessibility and visibility of fruits, vegetables, fried food, SSB, and activity-related stimuli/cues (e.g., stroller). Items are coded as "yes" or "no" on availability. Both instruments have been validated in the homes of families with children. The Home Food and Activity Environment Assessment may be completed in-person in the family's home or (if needed to abide by COVID-19 safety guidelines) by telephone.⁸²⁻⁸⁵

Caregiver-Child benchmark data and home visit completion data will be collected from the First Teacher Home Visiting Program to ensure the study does not affect family services. For this, First Teacher Home Visiting Program will provide us with their assessments that are done as part of the standard First Teacher Home Visiting Program yearly evaluations. These questionnaires are not part of our study assessments.

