8.3 STATISTICAL ANALYSES

At each time of measurement, descriptive statistics and measures of association will be used to summarize demographic characteristics and outcome measures. The analysis will also include graphical and statistical analysis of outlying observations and distributional characteristics of variables. Differences in outcomes of interest between the control and HABITS will be assessed by t-test of equal means and Chi-square test of equal proportions for continuous, ordinal, and categorical values, respectively.

For hypothesis 1 (primary outcomes), weight of mother or child between baseline and the 6-month and 12-month timepoints will be calculated and summarized by tabulating and plotting descriptive statistics by the study arms. Linear association of HABITS with weight changes will be estimated and adjusted for demographic information and other measured covariates by performing mixed regression models with home visitors as a random effect.

For hypothesis 2 (secondary outcomes), the analyses approach planned for Aim 1 will be used for determining if HABITS is associated with changes in maternal feeding practices, habit strength of targeted behaviors, or the household environments between baseline and 6- or 12-month follow-up.

Missing data will be addressed using multiple imputation and/or full information maximum likelihood estimation. Psychometric properties of the study scales will be investigated to ascertain appropriate validity and reliability. All statistical analyses will be performed using the most current version of SAS 9.4. Final results will be determined to be statistically significant when the accompanying statistical test yields a two-tailed probability of 0.05 or less.

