8.3.1 GENERAL APPROACH

At each time of measurement, descriptive statistics and measures of association will be used to summarize demographic characteristics and outcome measures. The analysis will also include graphical and statistical analysis of outlying observations and distributional characteristics of variables. Differences in outcomes of interest between the control and HABITS will be assessed by t-test of equal means and Chi-square test of equal proportions for continuous, ordinal, and categorical values, respectively. Primary and secondary outcomes will be assessed using mixed regression models with home visitors as a random effect with adjustment for relevant demographic information and other measured covariates.

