8.3.2 ANALYSIS OF THE PRIMARY ENDPOINT(S)

For the primary endpoints, weight of mother or child between baseline and the 6-month and 12-month timepoints will be calculated and summarized by tabulating and plotting descriptive statistics by the study arms. Linear association of HABITS with weight changes will be estimated and adjusted for demographic

information and other measured covariates by performing mixed regression models with home visitors as a random effect.

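### Section 3.2 calls home visit completion data necessary covariates, and the mixed models in 8.3 to 8.3.3 are not limited to baseline covariates, so the HABITS comparison may be conditioned on a post-assignment variable

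*Combined protocol and SAP*

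**What the plan says.** Section 3.2 separates primary completion (the last 12-month assessment) from the end of study. The end of study waits until benchmark and "home visit completion data have been received from our home visiting program partner, as these data will provide necessary covariates". It then adds, as a further reason, a check that family services are unaffected. Section 7.1 gives only that second purpose: "home visit completion data will be collected from the First Teacher Home Visiting Program to ensure the study does not affect family services".

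The models are described three times. Section 8.3 has weight change "adjusted for demographic information and other measured covariates by performing mixed regression models with home visitors as a random effect". Section 8.3.1 refers to "adjustment for relevant demographic information and other measured covariates" for primary and secondary outcomes. Section 8.3.2 repeats the wording for the primary endpoints, and 8.3.3 carries the same approach to the secondary endpoints. None of them lists the covariates, limits them to baseline, or says where visit data belong.

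On delivery, 3.1 says that families in the HABITS arm "will begin receiving the HABITS intervention at their home visits for 12-months", after the baseline assessment. Section 6.1 continues this "as long as they remain in the home visiting program". Section 5.1.2 says visits occur at least monthly and usually twice a month, with weekly HABITS check-ins between visits.

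On whether assignment may change visits, 2.3.1 reports that in preliminary work "participants were 27% less likely to discontinue home visiting services when they received the combined home visiting + obesity prevention curriculum". The same section says that families on the combined curriculum met the program's benchmark areas as often as the others.

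**The concern.** Hypotheses 1a and 1b compare families given HABITS with families given standard services. That is a total effect, and it includes anything HABITS does by keeping families in the program. Visit completion accrues after assignment and, in the HABITS arm, is part of the dose received. If it enters the mixed model, the arm coefficient compares families with equal numbers of visits.

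Two things can then go wrong. Any benefit that acts through retention is removed from the estimate. In addition, family circumstances that affect both visits and weight can bias the coefficient in either direction, even if visits themselves do nothing. Randomizing home visitors does not protect against this, and more participants would not remove it.

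**Working it through.** **Reading the sections together.** Section 3.2 gives the covariate role and the services check as two separate reasons, so the first cannot be read as the second. The mixed models are the only analyses for which the plan mentions covariates. An analyst following 3.2 and 8.3.2 could therefore reasonably put visits in the primary model, and nothing in the plan stops this.

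**The plan's own scale (8.2).** The target is 0.53 SD, with two-sided alpha 0.05 and 80% power.
- Normal-theory sample size: 2 × (1.96 + 0.84)² / 0.53² = 55.9, so 56 per arm.
- Inflation for clustering: 1 + (112/18 − 1) × 0.01 = 1.052, and 56 × 1.052 = 58.9, so 59 per arm.
- Attrition: 59 / 0.85 = 69.4, so 70 per arm, or 140 in total. The stated total reproduces if 59 is read as already inflated for clustering.
- Standard error with 59 per arm followed: √(2/59) = 0.184. With m = 118/18 = 6.56 the inflation factor is 1.056, giving 0.184 × √1.056 = 0.189 SD.

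**Assumptions for the size of the shift.** None of these is given for this trial.
- Control families leave the program with probability p = 0.15 to 0.50. The low end borrows the 15% study attrition in 8.2, which is a different quantity.
- HABITS families leave 27% less often (0.73p), using the figure in 2.3.1.
- Families who stay have 24 visits, and leaving times are uniform over the year.
- The within-arm correlation r between visits and favourable weight change is 0.1 to 0.5.

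**Arm difference in visits.** Mean = 24(1 − p) + 12p. Variance = 576(1 − p) + 192p − mean². The difference d is in pooled SDs.

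| p control / HABITS | Mean visits control / HABITS | Pooled SD | d |
|---|---|---|---|
| 0.15 / 0.1095 | 22.20 / 22.69 | 4.74 | 0.103 |
| 0.20 / 0.146 | 21.60 / 22.25 | 5.37 | 0.121 |
| 0.30 / 0.219 | 20.40 / 21.37 | 6.32 | 0.154 |
| 0.50 / 0.365 | 18.00 / 19.62 | 7.45 | 0.218 |

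**Equal r in both arms: shift = r × d.**
- Low: 0.1 × 0.103 = 0.010 SD (1.9% of 0.53).
- Central: 0.3 × 0.154 = 0.046 SD (8.7%). The estimate falls from 0.53 to 0.484, and 0.046 / 0.189 = 0.24 of a standard error.
- High: 0.5 × 0.218 = 0.109 SD (20.5%), leaving 0.421.

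**Visits related to weight only in the HABITS arm.** Shift = (r / SD₁) × V₁/(V₀ + V₁) × (mean₁ − mean₀), where 1 is HABITS and 0 is control.
- Low: (0.1 / 4.39) × 0.430 × 0.486 = 0.005 SD (0.9%).
- Central: (0.3 / 5.93) × 0.440 × 0.972 = 0.022 SD (4.1%), leaving 0.508.
- High: (0.5 / 7.13) × 0.459 × 1.62 = 0.052 SD (9.8%).

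**Monthly visits.** Section 5.1.2 allows some families monthly visits only. If 20% to 30% of families in each arm have 12 planned visits, d at p = 0.30 falls to 0.122 and 0.113. At r = 0.3 the shift is then 0.037 to 0.034 SD, or 0.19 to 0.18 of a standard error.

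**Confounding alone.** Suppose visits have no effect, but an unmeasured family factor raises visits by 0.3 SD and lowers weight by 0.3 SD per unit. The within-arm slope is then 0.3 × 0.3 = 0.09. With an arm difference of 0.2 SD in visits, the shift is 0.2 × 0.09 = 0.018 SD. If families who have more visits do worse on weight, the sign reverses.

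**Zero cases.** If d = 0 or r = 0 the shift is zero.

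**The case against.** The strongest reply is that 3.2 speaks of the statistical analyses in general and never names the primary model, and that 8.3.2 never names visit data. The plan has other uses for such variables: multiple imputation or full-information likelihood (8.3), and the mediation questions raised in 2.3.2. On this view the defect is only an unspecified covariate set. Part of this stands. A reader might infer that the primary comparison will be adjusted for visits, and the documents do not say so. What remains is that 3.2 states a covariate role for a post-assignment variable, and the models that take covariates are left open to it.

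The 27% figure is also weak support. It is not said to come from a randomized comparison, from HABITS itself, or from families who had already completed 90 days as this trial requires. No base rate or interval is given. It makes an arm difference in visits plausible but does not establish one.

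A reader might extend the point to all partner data. The initial 90-day benchmark precedes HABITS and is a legitimate covariate. Later yearly benchmarks follow assignment and should be kept out on principle, but 2.3.1 reports no difference between curricula in meeting benchmarks, so no bias from them is shown.

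Finally, visits are not the only delivery route, since weekly check-ins also carry HABITS. Giving every staying family 24 visits probably overstates d, as the monthly-visit calculation shows.

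**Conclusion.** The point holds in conditional form. Sections 3.2 and 8.3 to 8.3.3, read together, permit the arm comparison to be conditioned on visit completion. If assignment changes visits and visits relate to weight, the arm coefficient may not estimate the effect in hypotheses 1a and 1b.

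The size rests entirely on the assumptions listed. The central cases, about 0.03 to 0.05 SD, are systematic but modest. The 0.11 SD extreme needs 50% control discontinuation and r = 0.5.

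A reader might infer a serious loss of effect or power, for example an estimate falling to 0.29 SD. That needs an arm difference of 0.6 SD in visits and a slope of 0.4 (0.53 − 0.6 × 0.4 = 0.29). The 27% figure gives a difference of only 0.10 to 0.22 SD, so the documents do not support that reading. The case for change is that the wrong quantity might be estimated and that this is easily prevented. The change should be made before analysis; confidence is medium.

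**What to change.** In 8.3.2, and so by reference in 8.3.3, state that the primary and secondary mixed models adjust only for variables measured before HABITS starts. List them, for example the baseline value of the outcome, child age, demographics and the initial 90-day benchmark.

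In 3.2, state that home visit completion and later benchmark data are used only for the family-services check in 7.1, to describe delivery, as auxiliary variables in multiple imputation, or in a labelled exploratory dose analysis.

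This takes about one sentence in each section and no new data. Dose questions become exploratory. Leaving visits out forgoes a fall in residual variance of about r², which is 1% to 25% for r = 0.1 to 0.5 and 9% at r = 0.3. The possible loss of precision is therefore small at the central value.

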4 STUDY POPULATION

4.1 INCLUSION CRITERIA

Families enrolled in home visiting will be invited to participate in the study, with limited exclusion criteria. Caregiver-child dyads will be eligible to participate regardless of weight status because the targeted health behaviors are relevant and beneficial for all caregivers and children. Improvements in maternal behaviors (regardless of weight status) may further reduce children's obesity risk. To be included, caregiver-child dyads will have to meet the following inclusion criteria:

- Caregiver enrolling in the trial is 18 years of age or older
- Child is 0-5 years of age
- Child has at least 1 year of eligibility remaining in the home visiting program
- Family has completed their first 90-days in the home visiting program

4.2 EXCLUSION CRITERIA

- Child has a current or prior history of a feeding or growth disorder
- Caregiver has lost a significant amount of weight (>15 pounds) in the past 6 months unrelated to childbirth

4.3 SCREEN FAILURES

Caregiver-child dyads who do not meet study inclusion criteria will be informed of this decision by their parent educator and reassured that their family will still be in the home visiting program and this will not change the quality of the services and care you receive.

4.4 STRATEGIES FOR RECRUITMENT AND RETENTION

Individuals who are enrolled in the First Teacher Home Visiting program and who have completed their initial 90-day home visiting program benchmark testing will constitute our initial recruitment pool. Home visitors will approach their families who are potentially eligible to introduce the study, gauge interest, and screen interested families for eligibility. Designated study staff determine of families are eligible based on the completed screening form and inclusion/exclusion criteria. Home visitors are informed of family's eligibility and notify the family. Eligible families are then introduced to a blinded study assessment worker who schedules the enrollment and baseline visit.

The unique relationship between home visitors and mothers facilitates retention. Many of these caregivers are socially isolated and home visitors are important sources of support. We will also use strategies (implemented with participants in both intervention arms) that we have found effective for retention: (1) providing gift cards of \$100 at each data collection for all caregivers, with all incentives paid after each assessment; (2) ensuring frequent contacts with all participants to maintain engagement and foster open communication; (3) sending holiday newsletters to update participants about study activities; (4) acknowledging birthdays and milestones; (5) providing reminder phone calls before assessment sessions; and (6) seeking contact information of relatives or friends to be able to reach participants.

5 STUDY INTERVENTION

5.1 STUDY INTERVENTION(S) ADMINISTRATION

5.1.1 STUDY INTERVENTION DESCRIPTION

Table 1 outlines the components of the two study arms.

Table 1. Components of each study arm	Standard home visiting (Control Group)	Standard home visiting + HABITS (Intervention Group)
Early childhood education and school readiness	X	X
Parenting	X	X
Socioemotional development (e.g., regulate emotion & behavior, develop empathy)	X	X
Physical development (e.g., immunization; motor skills)	X	X
Limit fried foods		X
Limit sugar-sweetened beverages		X
Increase daily steps		X
Increase non-starchy vegetables and fruits		X
Self-monitoring of weight and target behaviors (caregivers only)		X

Standard home visiting curriculum. Our partner home visiting program, First Teacher Home Visiting Program meets the Department of Health and Human Services (DHHS) criteria for an evidence-based early childhood home visiting service delivery model (<http://homvee.acf.hhs.gov>). Caregivers and children receive monthly or bi-monthly visits and they are provided with a set of carefully developed curriculum, books and materials designed to strengthen children's cognitive skills, early literacy skills, social/emotional and physical development. These voluntary services are free of charge for mothers and children (ages 0-5 years) most at risk of disparities because of poverty, social isolation, lack of material and social support, lack of transportation and limited education and literacy.

HABITS curriculum (Intervention). HABITS focuses on healthy weight of all mothers, regardless of baseline weight status, and on preventing obesity through the promotion of healthy behaviors in early childhood. Accordingly, HABITS addresses habit-formation of four behaviors relevant to mothers and children: (1) limit fried foods; (2) limit sugar-sweetened beverages (SSB); (3) increase daily steps; and (4) increase fruits and vegetables (Table 2). These behaviors are consistently associated with long-term weight management, are amenable to habit formation, and have health benefits for all mothers and children, regardless of weight status (i.e., eating fruits and vegetables as substitutes for energy-dense fried foods benefit everyone, not only obese individuals). HABITS also addresses mothers' self-monitoring of weight and targeted behaviors to support habit-formation of eating/activity behaviors. Regular self-weighing and completion of food/activity records are associated with program adherence and successful weight management.

HABITS is also ecologically relevant in strategically modifying contextual cues in the home environment (choice architecture) to support habit-formation of targeted behaviors (e.g., acquiring and preparing fruits and vegetables is a prerequisite to automatically consuming fruits and vegetables). Specifically, the intervention targets three features of choice architecture relevant to the 5 behaviors targeted by HABITS: (1) availability (i.e., items exist in the home regardless of whether they are readily visible or accessible), (2) accessibility (i.e., items are easily retrievable, ready to use/eat, located within reach), and (3) visibility (i.e., items are easy to see on countertop, or when opening the refrigerator, freezer or cupboard in the case of foods/beverages; or visible by the door or other location in the case of walking-related stimuli/cues and self-monitoring materials).

Table 2. HABITS target behaviors, scientific premises and intervention description

Scientific premise	Intervention
Behavior #1: Limit fried foods	
Fried foods are energy-dense and contain a large amount of saturated fat. Higher consumption of high-saturated fat is associated with greater weight gain and poorer health.	
Habit-formation: Mothers will be provided corrective feedback and instruction to recognize fried foods, adopt alternative cooking methods, and modify their favorite recipes. Didactic learning and recommendations will be supported by experiential, hands-on and learn-by-doing practice activities involving both mothers and children. Food selection and cooking methods will then be repeated until mastery and automaticity are reached. Similar habits will be shaped, practiced, and repeated to address food selection outside the home. Home environment: The foods available at home and knowledge of cooking methods are key determinants of mothers' and children's food choices. Mothers will be encouraged to avoid bringing pre-made fried foods into the home, limiting access to ingredients necessary for frying foods, and promoting access to recipes and ingredients for alternative cooking methods.

Behavior #2: Limit sugar-sweetened beverages (SSB)	
Higher SSB consumption, which may lead to excess energy intake, is associated with greater weight gain and poorer health. Guidelines recommend that adults limit their SSB consumption and that fruit juice be limited to <4 ounces/day for children under the age of 3.	
Habit-formation: Mothers will be taught to decrease SSB consumption for themselves and their child by making water consumption a habit (e.g., consuming water at every meal) and providing alternative non-sweetened beverages. Home environment: Mothers will be taught to avoid buying or storing SSB at home. When SSB are present in the home, mothers will identify an inconvenient/inaccessible/hidden location for storage.

Behavior #3: Increase daily steps	
Guidelines recommend adults engage in 150 minutes of moderate intensity physical activity/week. Walking is easily performed and does not require specific skills or equipment. Walking 10,000 steps/day is consistent with ~60 minutes of brisk walking. Guidelines for infants (6-12 months): daily planned activities, like tummy time, 30 minutes/day of supervised but free play, and the opportunity to crawl and move around. Toddlers & Preschoolers (1-3 years): active for at	
Habit-formation: Mothers will be given pedometers and instructed to work towards accumulating 10,000 steps/day in making walking a habit in response to family-relevant cues and contexts. Mothers will receive corrective feedback to help them recognize contextual cues eliciting lifestyle activities. For example, "stairs" or "talking on the phone" will become cues eliciting "walking up the stairs" or "pacing while on the phone". Mothers will be coached to make children's activity/play a daily habit integrated in the family routine and in response to daily habitual cues or contexts (e.g., 10-min of play after breakfast). Home environment: Lack of resources and safety are salient barriers to physical activity. The choice architecture of the larger family environment (home & neighborhood) will be addressed in helping mothers design and select activities around their local environment, schedule, and preferences, and to optimize their use of safe spaces. Mothers will be provided with information about resources and

least 1 hour/day (2-3 hours or more is better), and avoid sitting or lying down for >1 hour at a time, except when sleeping. Young children (4-6 years): at least 1 hour/day of physical activity (up to several hours) and avoid sitting or lying down for >2 hours at a time, except when sleeping.
	
free group activities conducive to physical activity (e.g., parks, walking clubs, outings), and classes they can take with their children and other home visiting families. We also consider mothers as key social contributors of children's choice in providing access and opportunities for their children to be physically active.

Behavior #4: Increase intake of non-starchy vegetables and fruits
	

Fruits and vegetables are low in energy density, high in fiber, and generally contain more nutrients than other food groups. Eating low-energy dense fruits and vegetables daily as substitutes for high energy-dense alternatives can help individuals feel satisfied while reducing overall energy intake.^{29,30} Most children and adults eat fewer fruit and vegetable servings than are recommended, and children are more likely to consume fruits and vegetables if these foods are introduced early. The most simplified version of the USDA's recommendation is to fill half of the plate with fruits and vegetables for every meal and each snack. This simple visual guideline does not require any counting or measuring of food.
	
Habit-formation: Mothers will be instructed to consistently consume fruits and non-starchy vegetables as snacks (cue/ context) and to provide non-starchy fruits and vegetables at every meal (cue/ context). To do so, mothers will learn to (1) recognize snacks and meals as contextual cues eliciting fruits and vegetables consumption, and (2) prepare/cook/store non-starchy fruits and vegetables for themselves and for their young children. Corrective feedback from home visitors will be supported by learn-by-doing, hands-on activities such as taste tests and food preparation, cooking and storing demonstrations involving both mothers and children to promote multi-sensory exposure and increase children's acceptance of novel fruits and vegetables. Home environment: Families enrolled in home visiting programs receive assistance from WIC and the food bank. These organizations help promote fruits and vegetables availability for mothers and their young children. However, lack of exposure and knowledge on how to prepare and store these foods are critical constraints influencing these mothers and children's nutritional choices. Home visitors will work with mothers to ensure that the fresh, frozen, and/or canned fruits and vegetables they receive from WIC and the food bank are properly prepared, readily available, highly visible, and easily accessible in the home (e.g., prepared for convenience). Proper food preparation and storage (e.g., freezing) can also reduce food waste of perishable fruits and vegetables and ensure that families have fruits and vegetables available throughout the month. For example, cooking and freezing meals containing fruits and vegetables ensure availability despite financial constraints near the end of the month.


Behavior #5: Self-monitoring of weight and targeted behaviors (mothers only)
	

Grounded in self-regulation theory, self-monitoring of weight and related behaviors (e.g., food intake) provides immediate feedback, allows for corrective actions, and are foundational components of evidence-based weight management programs. Regular self-weighing and completion of food/activity records are associated with program adherence and successful weight management.
	
Habit-formation: Mothers will receive simplified self-monitoring forms with instruction to record weight and HABITS behaviors daily: number of fried foods, SSB, steps, and F/V servings. They will practice monitoring with their home visitors who will provide corrective feedback. Mothers will be instructed to weigh themselves at the same time each day in the same context (e.g., in the bathroom after brushing teeth). Similarly, they will be instructed to pair dietary self-monitoring with meals/snacks and to write down their step counts before bed (cue/context). Home environment: Mothers will be encouraged to place scales in highly visible and accessible locations, in close proximity to cues eliciting other well-established behaviors (e.g., beside the toilet). Mothers will be instructed to keep their self-monitoring checklist with them to ensure tracking occurs in close temporal proximity with the target behavior. Additional tips will be discussed, such as taking a picture of one's meal for later recording when necessary. With support and guidance from home visitors, posting of weight and target behavior graphs in visible locations (e.g., bathroom mirror, refrigerator door) to monitor progress will also be encouraged.

